3. **Pilot (revised):** To evaluate acceptability, feasibility, and outcomes of the intervention components:
  - a. Intervention: Compare women randomized to the virtual group-interactive workshop with those randomized to individually-accessed links to a PrEP promotional video and PrEP information on the ***primary outcome of having an individual discussion with the study nurse about the possibility of taking up PrEP; undergoing HIV self-testing guided by the study nurse (either in-person at the GHRU office or via telehealth visit) (secondary outcome); if eligible for PrEP, initiating PrEP (secondary outcome),*** and, for all women, changes in hypothesized mediators (information, risk perception, gender barriers, outcome beliefs, PrEP-stigma, peer norms) post-intervention and at 3-month follow-up.
  - b. Peer-driven recruitment: 1) Assess ***acceptability and feasibility*** of peer-driven recruitment (PDR) using pre-specified performance criteria for acceptance and recruitment (on average  $\geq 50\%$  attendees agree to recruit other women (i.e., become Peer Health Advocates [PHAs] and  $\geq 2$  recruits/PHA enroll in the study); and 2) evaluate ***reach*** of PDR (percent who score high on HIV risk assessment; percent who never tested or never attended family planning).

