## Data Analysis

Workshops: Compare women randomized to the virtual group-interactive workshop with those randomized to individually-accessed links to a PrEP promotional video and PrEP information on the **primary outcome of having an individual discussion with the study nurse about the possibility of taking up PrEP; undergoing HIV self-testing guided by the study nurse (either in-person at the GHRU office or via telehealth visit) (secondary outcome); if eligible for PrEP, initiating PrEP (secondary outcome)**, and, for all women, changes in hypothesized mediators (information, risk perception, gender barriers, outcome beliefs, PrEP-stigma, peer norms) post-intervention and at 3-month follow-up.)

To compare the **primary and secondary outcomes** across the two workshop conditions, we will use generalized linear models (GLM) with a logit link function and the method of generalized estimating equations (GEE) to account for the effect of clustering within recruitment chain. The logit link function is appropriate because the primary and secondary outcomes are dichotomous and characterized as yes/no if achieved at any time over the course of the study by the time of the 3-month follow-up interview. Intervention condition (Gender-Enhanced or Individual Access) is the primary predictor. Although the original data analysis plan also specified accounting for clustering by workshop group attended, we will not account for clustering by workshop group because women in the IA condition received the intervention as individuals rather than as groups.

We will adjust for any substantial baseline differences by condition on age. We will also adjust for any substantial differences by other demographic and behavioral characteristics, such as education level, whether attending school, has a primary partner, sexual risk behaviors (to be defined), relationship power, reported intimate partner violence if these factors differ substantially by condition at baseline and are also associated with the outcome (i.e., meet the conditions of confounding).

To assess if being a PHA, i.e., talking to other women about HIV prevention serves as an additional intervention dose, a secondary analysis will include a variable for whether the woman served as a PHA and recruited other workshop attendees (yes/no).

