**Mediators.** “Other outcomes” include those measures designed to tap constructs that are hypothesized in our theoretical model to be mediators, i.e., on the pathway between the intervention and the outcome. These are factors that we believe influence the outcome (women considering PrEP for themselves) and that if changed by the intervention will lead to an increase in this outcome. We want to know if these factors are influenced by the gender-enhanced intervention and help explain (mediate) any changes in the main outcomes. These hypothesized mediators, most of which are summary measures from multi-item scales, include PrEP information, perceived risk for HIV, perceived effectiveness of PrEP, positive outcomes of taking PrEP, gendered HIV prevention barriers related to partner disclosure, PrEP-related stigma, normative beliefs, medication beliefs. Please see the related document entitled “Table of pilot study measures 2022 June 22.” for descriptions.

An additional variable—stage of change for adopting PrEP--was added when we revised the study. This will also be considered a mediator, although at 3month followup, the last option of this measure is “I am taking PrEP”. This is the indicator for the outcome of initiating PrEP.

For the mediators, we will first test if the intervention had any effect on them, using generalized linear models (GLM) with an identity link function and GEE (to account for clustering effects) to compare the mean difference between the two intervention groups from post-test to pre-test, and from 3-month follow-up to post-test, to determine if there is an increase, decrease, or no change over time (difference of difference analysis), adjusting for age and other confounders if necessary. As per [name]: the model is of the form:

$E(Y|X,T1,T2)=\text{constant}+b1*X+b2*T1+b3*T2+b4*X*T1+b5*X*T2$ , where X is the intervention indicator, T1 and T2 are post-intervention and 3-month FU indicator respectively. The regression coefficient b4 represents the group difference in change of the outcome Y (i.e., the potential mediators) from pre- to

post-intervention, however, it is b5-b4 (NOT b5) that represents the group difference in change of Y from post-intervention to 3-month FU.

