As a second step, we want to know whether, apart from the intervention, any of the hypothesized mediators are associated with the outcomes, e.g., whether women who at pre-test have low PrEP stigma, high perceived risk, low gender barriers for example, were more likely to have a nurse conversation, undergo HIV testing, initiate PrEP. These analyses will be conducted adjusting for intervention condition.

Finally, any mediators that are altered by the intervention will be included in the earlier models testing intervention effects of gender-enhanced intervention on primary study outcomes. A substantial reduction in the estimate of effect for the gender-enhanced intervention once the mediator is included in the model gives evidence that the hypothesized mediator explains in part the effect, i.e., that the intervention worked, for example, by reducing PrEP stigma or increasing risk for HIV.

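### The mediator plan tests change up to post-test and change after it, but gives no test or interval for the effect from pre-test to 3 months (b5)

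*SAP*

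**What the plan says.** Aim 3a, as revised in December 2020 and repeated under Data Analysis in the SAP, compares the two conditions on changes in the hypothesized mediators "post-intervention and at 3-month follow-up". The protocol (Specific Aims and Hypotheses, Aim 3a) names the same two time points.

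The Mediators paragraph of the SAP's Data Analysis section first asks whether the intervention affected the mediators at all. It uses an identity-link GEE to compare the arms on change "from post-test to pre-test, and from 3-month follow-up to post-test", and the purpose is "to determine if there is an increase, decrease, or no change over time (difference of difference analysis"). The model contains condition, two time indicators and their interactions, "where X is the intervention indicator, T1 and T2 are post-intervention and 3-month FU indicator respectively", so pre-test is the reference time. On interpretation it says "The regression coefficient b4 represents the group difference in change of the outcome Y" from pre- to post-intervention, and then that "it is b5-b4 (NOT b5) that represents the group difference in change of Y from post-intervention to 3-month FU".

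The SAP's section taken from the original proposal (3.3.9.3) uses the same two intervals. Neither document assigns b5 a test or an interval. A later step says that "any mediators that are altered by the intervention will be included in the earlier models", without naming the contrast that decides which mediators qualify.

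**The concern.** Aim 3a names two time points, post-intervention and 3 months. The plan has a direct contrast for the first only. Its one contrast that uses the 3-month data is measured from post-test, so it asks whether the group difference moved after the intervention. Whether a difference from pre-test exists at 3 months is a separate question.

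Three patterns show what is at stake. If a gain is fully kept, b5-b4 is zero, and the report has no interval showing the effect that remains. If half is lost, b5-b4 is negative while a benefit remains, and again that benefit has no planned interval. If a gain builds slowly, it is split over two contrasts and each may miss it. The pilot is meant to inform a larger trial, and the SAP's Power Considerations put estimation with intervals ahead of testing, so the missing 3-month estimate matters more than a missing p-value.

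**Working it through.** **Algebra.** Under the SAP's model the Gender-Enhanced minus Individual Access difference in means is:

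- pre-test: b1
- post-test: b1 + b4
- 3 months: b1 + b5

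So pre to post is (b1 + b4) - b1 = b4. Post to 3 months is (b1 + b5) - (b1 + b4) = b5 - b4, which reproduces the SAP's statement. Pre to 3 months is (b1 + b5) - b1 = b5, which is not among the planned contrasts.

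**Inputs for size.** The SAP gives 100 participants, taken here as 50 per arm. Two-sided 0.05 is stated for the primary null hypotheses and assumed here for the mediators. The documents give no effect size for the mediators and no correlation between time points. I assume effects in SD units and a correlation r between any two time points, with r = 0.5 as the central value and 0.3 to 0.7 as the range. Dropout is ignored.

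**Standard error.** For any of the three contrasts, SE = sqrt(2(1 - r)) × sqrt(2/50). At r = 0.5 this is 1 × 0.20 = 0.20 SD. Power is approximately Φ(|effect|/SE - 1.96).

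**Gradual gain (0.3 SD at post-test, 0.6 SD at 3 months).** Here b4 = 0.3, b5 - b4 = 0.3 and b5 = 0.6. At r = 0.5, each planned contrast has Φ(1.5 - 1.96) = 32%, and b5 has Φ(3.0 - 1.96) = 85%.

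| Assumption | SE | b4 | b5-b4 | b5 |
|---|---|---|---|---|
| r = 0.3 | 0.237 | 24% | 24% | 72% |
| r = 0.5 | 0.200 | 32% | 32% | 85% |
| r = 0.7 | 0.155 | 49% | 49% | 97% |
| r = 0.5, design effect 1.525 | 0.247 | 23% | 23% | 68% |

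The last row allows for recruitment chains. With 100 women in 16 seed chains (protocol, recruitment waves table) the mean chain size is 6.25. With the intra-chain correlation of 0.1 that the SAP uses as an upper limit for its primary outcome, the design effect is 1 + (6.25 - 1) × 0.1 = 1.525. At r = 0.5 without clustering, the chance that at least one planned contrast is significant cannot exceed 32% + 32% = 64%, still below 85%.

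**Gain fully kept (0.6 SD at both times, r = 0.5).** b4 has 85% power and so does b5. b5-b4 is truly zero, so it rejects about 5% of the time. A GEE simulation of 400 runs gave 87% for b4, 84% for b5 and 7% for b5-b4.

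**Why a non-significant b5-b4 does not show maintenance.** At r = 0.5 its 95% interval has half-width 1.96 × 0.20 = 0.39 SD. Centred on zero, that interval still allows a loss of 0.39/0.6 = 65% of a 0.6 SD gain.

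**Why the two planned intervals do not give the third.** The point estimates add up to b5, but the variances do not. Both contrasts use the post-test value, with opposite signs. At r = 0.5 each has variance 0.04 and their covariance is -0.02, so Var(b5) = 0.04 + 0.04 - 2 × 0.02 = 0.04. Ignoring the covariance would give sqrt(0.08) = 0.28 instead of the correct SE of 0.20.

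**The case against.** A reader might infer that a gain kept in full would be reported as no effect. The plan does not support that. The two contrasts are reported together, and a kept gain shows as a positive b4 with b5-b4 near zero. b4 has the same power for that gain as b5 would have. The 5% rejection rate of b5-b4 is then the type I error of a true null, so it should not be counted as lost power.

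A reader might also infer that a half-kept gain would be declared a decrease. With b5-b4 = -0.3 SD that would reach significance only about 32% of the time, or 23% with the design effect above. b5 = +0.3 SD has the same power, so naming b5 would not rescue that case by testing. It would supply the estimate and its interval.

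The SAP's remark that the contrast is not b5 is a correct warning about what a coefficient means and does not forbid reporting b5. The SAP also promises interval estimates for parameters of interest and summary statistics by condition, so 3-month information is not wholly confined to b5-b4. Changes over successive intervals are a possible reading of the aim. For the mediation step, b4 is arguably better ordered in time, because the request to speak with the nurse is first elicited at the post-assessment and a 3-month mediator value may follow the outcome. That step is not restricted to b5-b4 either, so a mediator with a positive b4 can enter it.

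All of this stands and narrows the point. It does not supply the missing item: no sentence names b5 as a parameter of interest, and there is no rule for reading b4 and b5-b4 together as evidence about 3 months.

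**Conclusion.** The point holds as a gap in the planned contrasts. The SAP's algebra is correct, and an effect present at post-test is tested properly. Missing is a named test or interval for the group difference in change from pre-test to 3 months, although the aim asks about mediator changes at that time.

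The practical loss is greatest for gains that build after post-test: about 32% power on each planned contrast against about 85% on b5 in the central case, and 23% against 68% with chain clustering. These figures rest on assumed effects of 0.3 and 0.6 SD, r = 0.5, 50 women per arm and no dropout. The documents do not say that a gradual pattern is expected. The identities need none of these assumptions. The mediators are not the primary outcome and the pilot is not built around hypothesis tests, so this is a worthwhile correction to the analysis of a secondary question and does not threaten the main comparison.

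**What to change.** In the Mediators paragraph of the SAP's Data Analysis section, add that b5, the group difference in change from pre-test to 3 months, is the 3-month mediator effect and will be reported with its 95% CI. Keep b4 as the post-intervention effect. Keep b5-b4 as a secondary contrast for maintenance or decay, and state that a non-significant b5-b4 will not be read as evidence of maintenance.

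No new data or model is needed, since b5 is already a coefficient of the stated model. The cost is a short addition to the text and one more reported contrast per mediator: nine in all, from the eight constructs that the SAP lists plus stage of change. Because the SAP already carries subgroup counts in an update of December 2022, the change should be dated and marked as an addition.

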Sexual risk. High-risk will be defined as having unprotected vaginal or anal intercourse with a partner of unknown or HIV-positive status. Other risk factors considered will include number of partners (and number of HIV+ or unknown status) with whom one has unprotected sex, having a partner 10 or more years older or aged 35-44, experiencing IPV, social network members engage in transactional sex and/or experience IPV.

Hypothesized mediators and effect modifiers to be ascertained at each assessment include **PrEP information**-what PrEP is, common side effects, consequences of PrEP nonadherence (sample items: *most PrEP-related side effects are short-term; PrEP is highly effective in preventing HIV when taken every day*). **Perceived risk** will be assessed with the Perceived Risk of HIV scale ( $\alpha = .91$ ) (54) (sample item, *What is your gut feeling about how likely you are to get infected with HIV?*) (3), and modified to assess perceived risk for pregnancy. **Peer norms around PrEP** will be adapted from the 6-item social norm scale developed by Fernandez and colleagues ( $\alpha = .82$ ) (55) (sample items, *My partner/family would support my using PrEP*); **Positive and negative outcome expectancies of using PrEP** will be developed based on FG findings (e.g. *If I use PrEP, I will avoid conflict with my partner; my partner will object; my partner will abuse me; I will be less worried about getting HIV*), including items tapping **PrEP-related stigma** (e.g. *if I use PrEP, people will think I am promiscuous; people will think I am HIV-positive*); **PrEP attitudes**, developed from FG findings (*PrEP is a good option for me; I feel PrEP is safe to take; I feel PrEP will protect me from HIV*). **Gendered HIV prevention barriers** based on our work in a prior intervention trial (e.g., *it is the man's prerogative to use HIV protection or not; if I use HIV prevention it means I don't trust my partner; my partner could punish me*), and **self-efficacy for PrEP** (e.g., *I would be able to take the PrEP tablets every day even if I sometimes didn't feel well; if I worried that someone would see the tablets, I was short on time, I went to my boyfriend's house*). We also will assess relationship factors, including baseline experience of IPV (56), acceptability of IPV and endorsement of traditional gender norms in relationships (57). These factors may alter (modify) the effectiveness of the GE intervention.

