Power Considerations. The primary goal for this pilot work is to collect preliminary data regarding feasibility, acceptability and target outcomes for the proposed intervention. In line with guidelines from PA-17-166: *Formative and Pilot Intervention Research for Prevention and Treatment*, which caution against using pilot studies (where the sample size is of necessity small) to obtain an estimate of an effect size, we will use these pilot data to rule out unusually large or small true effects through standard 95% confidence interval procedures. We will confirm extrinsic effect sizes are contained within our confidence intervals from the pilot. We will examine the distribution of each variable, and calculate summary statistics by intervention condition. We will estimate key intervention parameters with sample means and proportions together with two-sided 95% confidence intervals, and test the primary null hypotheses at the traditional two-sided level  $\alpha=.05$  (simulation of the subsequent RCT). For planning the RCT, we will also consider one-sided 90% confidence limits for mission-critical *design parameters* such as standard deviations and reference group endpoint rates and proportions in the conservative direction. This is because we intend to plan sample size for the RCT so that power will be “excellent” (at least 80% power) for the clinically relevant effect size to be specified. This strategy will make proper allowance for the limited sample size of the pilot study with its consequent uncertainties, and still yield appropriate sample sizes for the RCT. “Mission-critical” parameters include proportions for dichotomous endpoints (uptake of PrEP clinical assessment, uptake of PrEP yes/no); means and standard deviations for continuous potential mediators of outcome (e.g. gender barriers, PrEP-stigma). Large sample sizes are not required to locate these parameters approximately, but adequately, for planning the subsequent trial, whereas testing the study hypothesis in the pilot

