will generally not have sufficient statistical power. Estimation of mission-critical design parameters with point and confidence interval estimates will be considered highly important; continuous outcome measures make it feasible to detect promising effect effects even in small samples. For the continuous measures, means and standard deviations (sd) will be estimated. For approximately normally distributed variables, an upper one-sided 90% confidence limit for the sd,  $\sigma_u$ , will be constructed from  $\sigma_u = s \chi^2_{v,10}^{1/2}$ , where s is the sample sd and  $\chi^2_{v,10}$  is the upper 10th percentile of the chi-squared distribution with v degrees of freedom. For approximately log-normally distributed variables, a logarithmic transformation will be applied to achieve approximate symmetry and normality. For the dichotomous variables (such as the primary and secondary outcomes, or the PDR performance criteria), exact binomial methods will be employed for the CIs for proportions. As an example, the width of the exact 95% confidence interval around a point estimate of 40% (e.g., percent women who score high-risk) would be 30%-50% with 100 participants.

While testing the primary null hypothesis is not the primary goal for this pilot study, if we assume the proportion of women who undergo PrEP clinical assessment in the information-only group ranges from 20% to 50%, with total sample size of 100 participants we are still able to declare a difference of 33 to 36 percentage points as statistically significant at 0.05 level with power of 80% if the within recruitment chain and within intervention-delivery group correlation coefficient is no greater than 0.1. As an illustration of how this can be used for planning the large randomized trial, suppose in this pilot study, proportion of participants take PrEP risk screening is 85% and 50% for Gender-Enhanced workshop and Information-Only Workshop respectively while the minimally clinically relevant improvement, on extrinsic grounds, is an improvement of 15 percentage points. Then, N=240 per group would be required in the RCT. The above plan will allow us to assess feasibility and acceptability, estimate factors influencing intervention parameters, and examine the range of possible effect sizes for our primary outcome. Therefore, the information collected from this pilot study should put us in an excellent position to conduct a future full-scale RCT.

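### The primary outcome model gives no pre-specified place to the pre-test PrEP scores that the SAP believes drive the outcome, so pre-test differences between arms can be read as a workshop effect

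*SAP*

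**What the plan says.** **Outcome model.** SAP, Data Analysis, fits a logit-link GEE to the primary and secondary outcomes, with condition (Gender-Enhanced, GE, or Individual Access, IA) as the main predictor and clustering on recruitment chain. Age is adjusted for if substantially imbalanced. Other demographic and behavioral characteristics are adjusted for "if these factors differ substantially by condition at baseline and are also associated with the outcome". The examples are education, schooling, primary partner, sexual risk, relationship power and partner violence. The list is open, but it names no PrEP score.

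**The scores.** SAP, Mediators, lists PrEP information, perceived risk, stigma, gendered barriers, normative beliefs and others, and says its authors believe these influence the outcome. A second-step analysis asks whether "women who at pre-test have low PrEP stigma, high perceived risk, low gender barriers for example, were more likely" to talk to the nurse, test for HIV or start PrEP, adjusting for condition. Mediators enter the outcome model later only if the intervention changed them, as a test of mediation.

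**Availability.** Protocol, Assessment Instruments (pilot study measures), begins its list of scales with "Hypothesized mediators and effect modifiers to be ascertained at each assessment", so pre-test values should exist.

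**Allocation.** Protocol, Study Procedures (pilot recruitment), randomises 16 seeds 1:1. Women in Waves 2 to 4 are invited to the condition their recruiter took part in.

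**The concern.** A pre-test variable that predicts the outcome and differs between arms moves an unadjusted comparison. The SAP names variables that it thinks predict the outcome, and gives them no planned role in the comparison where that matters. The confounder rule could be stretched to reach them, but only after the balance and the association with the outcome have been seen.

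The design raises the stakes above those of an individually randomised trial. With few randomised units and women recruiting their friends, the arms can differ through chance at seed level or through who recruits whom. GEE on chain adjusts the standard error for within-chain similarity; it does not correct a difference in starting point. The SAP's main question (December, 2020 Revisions) is whether the group workshop does more than individually accessed material to prompt women to consider PrEP. A prior difference in how women see PrEP or their own risk would be counted in the answer. The pilot's intervals and proportions are also meant to inform the later trial, where the SAP's worked example uses a 15-point improvement.

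**Working it through.** **Inputs from the documents** (SAP, Power Considerations): 100 women, taken as 50 per arm; "test the primary null hypotheses at the traditional two-sided level" of 0.05; 80% power; comparison rate "in the information-only group ranges from 20% to 50"%; "within intervention-delivery group correlation coefficient is no greater than 0.1". Seeds and waves: 16 + 28 + 28 + 28 = 100, so 84 women are recruits.

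**Assumptions** (not in the documents): strength of the score, cluster size, and similarity of scores within a chain.

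**1. The plan's own figure.** The SAP says "with total sample size of 100 participants we are still able to declare a difference of 33 to 36 percentage points". Take effective n per arm = 50/(1 + (m − 1) × 0.1) in a pooled-variance two-proportion test. Clusters of m = 7 give 32.9 to 34.8 points and m = 8 gives 33.8 to 35.8. The figure is reproduced, with no covariate in it.

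**2. Shift from a pre-test gap, no true effect.** To first order, shift = gap × R × √(p(1 − p)), where R is the score–outcome correlation and p the outcome rate. For example, 0.3 × 0.3 × √(0.5 × 0.5) = 0.045, or 4.5 points. Integrating a logistic model over a normal score, with a 0.3 SD gap:

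| Odds ratio per SD (assumed) | Shift, outcome rate 20% to 50% |
|---|---|
| 1.5 | 1.9 to 2.9 points |
| 2 | 3.1 to 4.7 points |
| 3 | 4.5 to 6.6 points |

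In simulation (1500 trials per setting) adjustment left about 0.5 point or less.

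**3. How often chance gives such a gap.** SE of the gap = √(2 × DE/50) in SD units. DE = 1.5 gives √0.06 = 0.245 and P(|gap| ≥ 0.3) = 22%. DE = 1.75 gives √0.07 = 0.265 and 26%. Peer selection would add to this by an amount that cannot be computed.

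**4. Scale against sampling error.** SE of the risk difference = √(2p(1 − p)DE/50). It runs from √(2 × 0.16 × 1.5/50) = 9.8 points to √(2 × 0.25 × 1.75/50) = 13.2 points.

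**5. Precision.** Multiplying the variance of the risk difference by (1 − R²):

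| R (assumed) | 33 to 36 points becomes | Equivalent unadjusted N, 100/(1 − R²) |
|---|---|---|
| 0.2 | 32.3 to 35.3 | 104 |
| 0.3 | 31.5 to 34.3 | 110 |
| 0.5 | 28.6 to 31.2 | 133 |

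Simulated logit GEE, 16 chains of 6, 600 runs per setting:

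| Log-odds slope per SD | Power unadjusted | Power adjusted |
|---|---|---|
| 0.4 | 80–85% | 81–87% |
| 0.7 | 77–79% | 81–83% |
| 1.2 | 68–71% | 77–79% |

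The SE of the log odds ratio rises with adjustment: about 0.47 to 0.49 at slope 0.4, and 0.45 to 0.54 at slope 1.2 (score uncorrelated within chains). Power still improves because the estimate moves further from zero.

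**6. False positives when balance is poor.** In null runs with scores correlated 0.2 within chains, the fifth of trials with the largest gap had 13–19% false positives unadjusted and 7–8% adjusted. Each such fifth is 120 trials, so these rates are rough. With scores uncorrelated within chains there was no consistent gain (8–14% against 8–13%).

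**The case against.** **A model with score and condition is already planned.** The second-step analysis contains both, whatever the balance. This stands in part. That model is aimed at the score's association; the SAP does not plan to report its condition coefficient as an adjusted GE effect.

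**The pre-test is not a clean baseline for most women.** Of 100 planned, 84 take it after contact with a GE- or IA-exposed recruiter who has PrEP material to hand out, and the protocol's rationale says chain referral may itself change norms. Their scores may already carry some GE effect, which adjustment would remove. This stands, and it is why the unadjusted result must stay.

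**Precision.** A reader might infer that leaving the scores out wastes substantial precision. The documents do not support this: they give no score strength, the gain is small unless prediction is strong, and on the planned log-odds scale the SE does not fall.

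**The scores are not prior PrEP interest.** The second step names stigma, perceived risk and gender barriers. Stage of change is closer to interest, but the documents do not show whether it is asked at pre-test. Eligibility also excludes women taking PrEP or planning to begin, which narrows prior interest, though not necessarily stigma or perceived risk. This stands.

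**Size and purpose.** A shift of 2 to 6.6 points is at most about two thirds of one SE, since 6.6 goes with a 50% rate and an SE of at least 12.2 (√(2 × 0.25 × 1.5/50)). Chance gaps are part of ordinary sampling error, and testing is not the pilot's main goal. This limits the weight of the point. It does not cover peer selection, which the SE does not describe.

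**Conclusion.** The point holds in a limited form. The primary model has no pre-specified place for pre-test scores that the SAP believes matter and that the protocol collects. The open covariate list could admit them only through a rule that looks at the data first. Because only seeds are randomised, a pre-test gap from chance or peer selection would be read as a workshop effect: about 2 to 6.6 points for a 0.3 SD gap, with chance alone producing a gap of at least that size in about 22% to 26% of trials. These sizes rest on assumed odds ratios of 1.5 to 3 per SD, outcome rates of 20% to 50% and a design effect of 1.5 to 1.75. The SAP's 0.1 limit is a power assumption; applying it to the scores is an assumption too.

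Two stronger readings should be resisted. One is that the SAP expects the second-step scores to predict nurse contact: that step poses a question, and the stated belief is in the Mediators text before it. The other is that the unadjusted analysis is wrong and should be replaced: for women in Waves 2 to 4 the unadjusted result keeps any effect of contact with the recruiter, and the adjusted one excludes it. This is a cheap improvement, not a fatal fault.

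**What to change.** In SAP, Data Analysis:

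- Name one or two scores confirmed to be collected at pre-test, for example perceived HIV risk or PrEP stigma; use stage of change only if it was asked then.
- Enter them in the outcome model whatever the observed balance or association.
- Report the adjusted GE effect as a standardised risk difference with its interval, and the planned unadjusted result beside it.
- State that for Wave 2 to 4 women the pre-test follows contact with an exposed recruiter, so the adjusted estimate excludes any effect of that contact.
- Record when the scores were chosen and what data had been seen. The Effect measure modifiers section, updated in December 2022, already shows observed subgroup counts, so a choice made after that date should be labelled accordingly.

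The cost is SAP wording and one extra model; no new data are needed. With about 100 women, the number of scores should stay at one or two.
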